In patients undergoing neurosurgical procedures, intraoperative blood loss is a very common problem that anesthesiologists encounter. Bleeding can result from dilated epidural venous plexus, soft tissue paraspinal blood vessels, tumor hypervascularity, and even uninvolved bone. [1] This massive amount of blood loss may lead to perioperative coagulopathy, and therefore use of allogeneic blood products such as: blood, platelets, and/or coagulation factors.[2] However, blood product transfusions are associated with significant complications that also need to be taken into consideration when thinking about transfusions; these involve, but are not limited to: infections, acute lung injury, organ dysfunction, and multiorgan failure. Therefore, an early and specific characterization of the cause of bleeding is crucial to achieve an effective and goal directed perioperative hemostatic therapy and reduce these types of complications. [3, 4]

The estimated blood loss is different between surgical procedures; in spinal fusion surgeries it has been documented to be between 650 to 2839 mL per patient, with transfusion requirements in 50% to 80% of the patients analyzed. [2] Patients undergoing surgical procedures for scoliosis had an estimated blood loss of 975.4 \pm 318.7 mL [5]; and in spine metastatic disease, a meta-analysis performed by Chen et al. showed blood loss ranges between 1100 ml to 6039 ml, with blood losses greater than 5000 ml present in 12% of the patients. [6]

This amount of bleeding warrants massive transfusion for resuscitation and requires an adequate hemostatic approach in order to prevent massive hemorrhage complications such as acidosis, hypothermia, and coagulopathy. In addition, it can also lead to surgical complications, such as incomplete spinal decompression, inadequate spinal fixation, poor neurologic outcomes, or death. [1]

Coagulopathy and/or uncontrolled bleeding are caused by defects on clot stability and firmness. Deficiency of coagulation factors, fibrinogen, and platelets lead to defects on clot firmness, while hyperfibrinolysis and factor XIII deficiency lead to decrease clot stability. Several studies have underscored the importance of avoiding acidosis, hypothermia, and coagulopathy; these studies have been performed mainly in cardiac surgery and trauma populations. [7]

For years, hemostatic therapy in massively bleeding and/or transfused patients has been guided with standard coagulation tests (SCTs) such as prothrombin time (PT), prothrombin index (PTI), activated partial thromboplastin time (aPTT), international normalized ratio (INR), fibrinogen, and platelet count. However SCTs limitations include the inability to assess clot strength, fibrinogen functionality; it does not measure the functionability of the red blood cells, and it does not assess the response of all these factors to an injury or surgery. Another potential disadvantage in these tests, includes the turnaround time; which generally is >30 minutes, ranging between 29 to 235 minutes. All these factors contribute to delay the clinical decision in this dynamic setting. [8-10]

Recently, point of care (POC) monitoring has emerged as a valuable alternative in hemostatic therapy algorithms for trauma, transplant, and cardiac surgeries. Thromboelastography (TEG) and thromboelastometry (ROTEM) are viscoelastic coagulation monitors that have shown to have the

Protocol #:2014H0447

Version: 1.0

potential to provide a more updated and comprehensive overview of the coagulation status. They provide a closer approach to *"in vivo* coagulation", by measuring the entire clot process starting from fibrin formation until clot retraction and degradation (fibrinolysis). [8]

Rotational thromboelastometry (ROTEM) is a POC testing device commonly used to provide a global assessment of the hemostatic status by measuring multiple aspects of blood coagulation, including, the generation of thrombin, factor deficiency, platelet function, fibrinogen, fibrinolysis and the effect of heparin in the coagulation cascade. ROTEM provides the development of the clot via initiation, increased clot firmness and changes of blood clotting under low shear conditions. ROTEM can also monitor the *extrinsic coagulation pathway* in the **EXTEM** assay and the *intrinsic coagulation pathway* in the **INTEM** assay by adding ellagic acid. [11]

Different modifications can be made to both the EXTEM and INTEM in order to assess other various defects of hemostasis:

- 1. Addition of Cytochalasin-D in the *EXTEM* directly measures the fibrin contribution to the clot and indirectly assesses fibrinogen availability; called **FIBTEM test.**
- 2. When compared to the *EXTEM* assay, the addition of Plasmin inhibitor confirms fibrinolysis and demonstrate efficacy of antifibrinolytic therapy: **APTEM test**.
- 3. Addition of Heparinase to *INTEM* assay, can help to discriminate heparin activity from an enzymatic factor deficiency: **HEPTEM test.**

Some other parameters can also be assessed by ROTEM. These include: clotting time, clot formation time, clot firmness, clot lysis, and A10 (which measures the amplitude at 10 minutes after the end of clotting time).

Several studies in trauma, cardiac surgery, postpartum hemorrhage, and scoliosis surgery have shown that maximum clot firmness (MCF) and fibrinogen levels are excellent predictors of perioperative bleeding complications and massive transfusion.[12] FIBTEM-A10 (Clot amplitude at 10 minutes after the end of clotting time) and FIBTEM MCF (maximum clot firmness) predict massive transfusion similarly to standard coagulation tests [13].

In cardiac surgeries, POC testing showed a lower cumulative dosage of packed erythrocytes, lower rate and smaller dose of fresh frozen plasma (FFP) and platelets concentrate (PC) transfusion. As well as reduced postoperative mechanical ventilation time, length of intensive care unit stay, composite adverse events rate, cost of hemostatic therapy, and 6-month mortality [3].

ROTEM standardized massive transfusion protocols have been used to successfully choose the optimal allogeneic blood product or coagulation factor concentrate, reduce transfusion requirements and reduce blood loss in cardiac surgery, transplant surgery, and massive trauma. The rapid ROTEM turnover has shown to impact a timely targeted hemostatic therapy and coagulopathy prevention [11, 14, 15].

Protocol #:2014H0447

Version: 1.0

The choice and amount of haemostatic therapy is not only highly relevant for patient outcomes but it is also highly relevant economically. Transfusion cost-benefit analysis has shown that the average cost of allogeneic blood replacement is \$250 per unit transfused, auto transfusion is \$270 per individual, and cell saver is \$512 per patient [11]. Recently, the analysis of the cumulative cost of hemostatic therapy comparing POC-guided therapy with conventional coagulation test guided therapy found that the mean cost of therapy is $1,528 \in (\$1,924)$ and $3,109 \in (\$3,914.76)$ per patient respectively [3].

II. OBJECTIVES

1. Primary objective

Compare the overall amount of intra-operative Red Blood Cells and Fresh Frozen Plasma guided with ROTEM versus laboratory coagulation tests in patients undergoing major spinal surgeries.

2. Secondary objectives

- Compare the amount of Cryoprecipitate and Platelets transfused intraoperative between both groups.
- Compare the amount of all blood products transfused at 6, 12, and 24 hours postoperative.
- Compare the incidence and requirements of fibrinogen concentrate, PCC, antithrombin concentrate, factor XIII concentrate, and activated recombinant factor VII, or any other hemostatic therapy. Compare variables that affect coagulopathy such as acidosis and hypothermia.
- Compare hemodynamic variables (BP, HR, O2, Temperature, Arterial blood gases) during surgery.
- Compare postoperative time of mechanical ventilation
- Compare length of ICU stay and overall hospital stay
- Compare total in hospital need for transfusion
- Compare postoperative coagulation status on days 1 and 3 if available
- Compare overall infection rate
- Compare 30 days mortality

3. Exploratory objectives

Compare the total costs of intra-operative blood transfusion guided with ROTEM versus laboratory coagulation tests in patients undergoing major spinal surgeries.

III. Material and methods

1. Study design:

This is a prospective, randomized parallel-group, single center study in patients undergoing elective major spine surgery. Patients will be randomized to guide blood transfusion administration with ROTEM or laboratory coagulation tests (ABG, PT, PTT, aPTT, Hb, platelets,

Version: 1.0

and fibrinogen). Randomization list will be computer-generated using a balanced allocation ratio 1:1.

- 2. Inclusion and exclusion criteria:
- Inclusion criteria
- 1. Male or female age 18 years or older.
- 2. Able to provide inform consent.
- 3. Patients schedule to undergo elective major spinal, orthopedic, or combined procedures under general anesthesia that are expected to receive intraoperative blood products and last greater than 2 hours.
- Exclusion criteria
 - 1. Subjects younger than 18 years old.
 - 2. Subjects who are prisoners.
 - 3. Subjects who refuse transfusion of blood products.
 - 4. Subjects unable to participate in the study for any reason in the opinion of the Principal Investigator.
 - 5. Subject with past medical history of uncontrolled coagulopathies.

3. Study population and sample size:

The power analysis has been calculated based on a mean estimated RBC transfusion of 8 units with a conservatively estimated standard deviation of 5. We expect that ROTEM will decrease the RBC transfusion by 3 units. We make the same assumptions for FFP. We will test each main outcome between the ROTEM and control groups at an alpha of 0.025 (adjusted for 2 main outcomes). We need 110 patients; 55 patients in each group to achieve 80% power to detect a difference of 3 units assuming a standard deviation of 5 at an alpha of 0.025.[3,13]

4. Randomization and study procedures:

Patients will be randomized in a 1:1 ratio to either laboratory coagulation tests or ROTEM. No changes in surgery or anesthesia technique will be made for study's purposes.

a. Laboratory Coagulation Tests

If the patient is randomized to laboratory coagulation tests, anesthesia care providers will assess the hemostatic status according to OSUWMC standard practices and their own clinical criteria.

Laboratory coagulation tests include but are not limited to the following: hemoglobin, platelet count, fibrinogen concentration, INR, aPTT, and PT. These assessments will be performed at fixed perioperative time points (preoperatively, every 2 hours intraoperatively, end of surgery (EOS), and 24 hours after EOS). Intraoperative arterial blood gases will be performed repetitively

Protocol #:2014H0447 Version: 1.0 at a fixed range (every hour) based on anesthesia care provider's decision, along with any other common laboratory tests.

b. ROTEM

If the patient is randomized to ROTEM, the anesthesia care provider will be blinded to any conventional intraoperative coagulation test that might be performed during surgery.

ROTEM will be used according to the manufacturer's instructions using equipment and test reagents provided by Tem International GmbH. All tests will be performed at the bedside by a healthcare provider trained to perform ROTEM. A specific algorithm has been created by [name] (Clinical Director at Tem International GmbH-ROTEM) and should be followed according to measurements obtained during surgery (Figure 1).

ROTEM monitoring will be performed in patients with signs of clinically relevant diffuse bleeding and in whom blood transfusion is considered (Temp >35°C; pH <7.2; Cai >4.6 mg/dL; Hb \ge 9g/dL, or >10g/dL with anticipated greater blood loss) or at a fixed range every 2 hours or at Anesthesiologist criteria based on patient's clinical situation.

Patient's clinical situation should be consider as the most important component on the transfusion decision-making process. Packed erythrocytes will be transfused to maintain hemoglobin concentrations >9g/dl or >10g/dl in individuals with underlying cardiovascular disease or anticipated greater blood loss. Individual based dynamics (tachycardia, hypotension, sings of ischemia on electrocardiogram, and lactic acidosis) strongly indicating the need for erythrocyte transfusion will be also part of the decision-making transfusion process by the anesthesia care provider.

5. Data collection

The following data points will be recorded in the interventional and control group patients:

- Demographic information (age, sex, height, weight, BMI, race)
- Medical History (including past and current diagnosis, use of chemotherapy or radiation, type of cancer, medications, surgical history)
- Surgical Information (Procedure type/reason for surgery, length of surgery, perioperative medications, ASA physical classification, type of anesthesia)
- Anesthesia record information
- Baseline (pre-operative) and perioperative coagulation lab values (PT, PTT, INR, HTC, HTC, PLT, FIB) (followed for 24 hours postoperatively)
- Perioperative ROTEM values
- Baseline and perioperative hemodynamics (BP, HR, RR, OXYGEN SATURATION, Temperature).
- Intraoperative arterial blood gases
- Intraoperative blood loss (over time)

Protocol #:2014H0447

Version: 1.0

- Transfusion information (type of product, number of transfused units, time administered) intraoperative and 6, 12, and 24 postoperative.
- Use of other hemostatic therapy
- Use of antifibrinolytic agents
- Intraoperative fluid management (type, volume, and frequency)
- Urine output for the first 24 hours.
- Postoperative time of mechanical ventilation
- Length of ICU stay and hospital stay
- Other intraoperative and postoperative complications (including respiratory failure, overall infection rate)
- Inpatient mortality
- Postoperative Day 30 phone call follow-up to assess serious adverse events and mortality.
- Hemostatic therapy cost assessment

IV. Assessment and reporting of Adverse Events and Serious Adverse Events

The occurrence of adverse events (AE) and serious adverse events (SAE) will be recorded from the time of consent until discharge. For each AE, the relationship to the study procedures and monitoring, severity, expectedness, outcome will be determined by the PI and recorded in the study source accordingly

If the case a subject withdraws from the study due to a serious adverse event the local IRB will be notified within 10 days.

Adverse Event definition

An AE is defined as any untoward medical occurrence in a patient or clinical investigational subject who has undergone an investigational procedure and that does not necessarily have to have a causal relationship with the study treatment. An AE can be any unfavorable or unintended sign, symptom, abnormal laboratory finding, or a temporal disease associated with the study procedure and monitoring, whether or not considered related to the procedure. Planned hospital admissions and/or surgical operations for an illness or disease that existed prior the subject was enrolled in a clinical study are considered part of the subject's medical history and are not considered AEs.

Serious Adverse Event

A SAE is any untoward medical occurrence that at any dose:

- Results in death
- Is life-threatening
- Results in persistent or significant disability/incapacity
- Requires in-subject hospitalization or prolongs hospitalization

Version: 1.0

- A congenital anomaly/birth defect

- Is another medically-significant event that, based upon appropriate medical judgment, may jeopardize the subject and require medical or surgical intervention to prevent one of the outcomes listed above.

V. Withdrawal criteria from the study

Reasons for premature discontinuation

According with the Declaration of Helsinki, participants have the right to withdraw from the study at any time for any reason. The Principal Investigator also has the right to remove a subject from the study. Reasons that a subject may be removed from the study include:

- An AE or SAE

- The request of the subject, his/her legal representative or caregiver, or investigator, for administrative or other reasons

- Non -compliance with medication, protocol violation, or unreliable behavior

- Any clinically significant abnormalities identified by the Principal Investigator according to his clinical judgment will be followed by appropriate tests and/or procedures until these abnormalities have subsided, returned to to clinically-acceptable levels, or can be attributed to causes other than the study procedure.

The principal Investigator may withdraw an enrolled and treated subject from the study for any of the following reasons:

- Occurrence of a serious or intolerable adverse event
- Emergence of a clinically-significant change in laboratory parameters.
- The subject requests to be discontinued from the study

- A protocol violation sufficiently serious as to require subject withdrawal

[figure not shown]
- General or specific changes in the subject's condition that render further treatment unreasonable or unsafe within the standards of clinical practice in the judgment of the Principal Investigator or treating physician.

Any subject may leave the study at any time. If a subject decides to stop participating in the study, there will be no penalty. The subject will not lose any benefits to which they are otherwise entitled. Their decision will not affect their future relationship with The Ohio State University.

Protocol #:2014H0447

Version: 1.0

VI.Figure 1. ROTEM Spine Surgery Algorithm

- ¹ Basic conditions:
 - Temp. >35°C; pH >7.2; Cai++ >4.6 mg/dL.
 - $Hb \ge 9 g/dL$.
- ² Antifibrionolytic therapy:
 - Dirkmann et al. Anesth Analg. 2014 (under review)
 - CT_{FIB} > 600 s represents a flat-line in FIBTEM
 - Chapman et al. J Trauma Acute Care Surg. 2013
- ³ Fibrinogen dose calculation:

- A10_{FIB} 9-12 mm: 50 mg/kg fibrinogen
 (2.5 mL/kg fibrinogen conc. or 5 mL/kg cryoprecipitate)
- A10_{FIB} ≤ 8 mm: 75 mg/kg fibrinogen
 (3.75 mL/kg fibrinogen conc. or 7.5 mL/kg cryoprecipitate)
- ⁴ Platelet concentrate (PC) transfusion:
 - A10_{EX} 35-44 mm: 1 pooled or apheresis PC
 - \circ A10_{EX} < 35 mm: 2 pooled or apheresis PC
 - A10_{EX} \leq 25 mm: Platelet conc. + fibrinogen
- ⁵ If Prothrombin-Complex-Concentrate (PCC) is not available:
 - o 10-15 mL/kg FFP or
 - \circ 45-90 µg/kg rFVIIa (if A10_{EX} and A10_{FIB} are ok but FFP is not effective)
- Simultaneous interventions:
 - Maximum three interventions at the same time (In first analysis and severe bleeding)
 - Maximum two interventions at the same time (In second analysis and moderate to severe bleeding)
 - Only one intervention
 (In second or later analysis and mild to moderate bleeding)

Version: 1.0

Protocol #:2014H0447

Version: 1.0

VIII. REFERENCES

- 1. Bilsky, M.H. and J.F. Fraser, *Complication avoidance in vertebral column spine tumors*. Neurosurg Clin N Am, 2006. **17**(3): p. 317-29, vii.
- 2. Elgafy, H., et al., *Blood loss in major spine surgery: are there effective measures to decrease massive hemorrhage in major spine fusion surgery?* Spine (Phila Pa 1976), 2010. **35**(9 Suppl): p. S47-56.

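### Total in-hospital transfusion is a secondary objective, but the data list records transfused units only up to 24 hours after surgery

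*Combined protocol and SAP*

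**What the plan says.** Section II.2 (Secondary objectives) of the combined protocol and SAP lists two postoperative transfusion comparisons as separate items. One has fixed times: "Compare the amount of all blood products transfused at 6, 12, and 24 hours postoperative". The other covers the stay: "Compare total in hospital need for transfusion". The second is not defined further, so the text does not say whether need means units, any transfusion, or both.

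Section III.5 (Data collection) opens with "The following data points will be recorded in the interventional and control group patients". Its transfusion item reads "Transfusion information (type of product, number of transfused units, time administered) intraoperative and 6, 12, and 24 postoperative". The word hours is missing there, and I take it from II.2. The same list follows other outcomes over the whole stay: "Length of ICU stay and hospital stay" and "Inpatient mortality".

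On safety, section IV records adverse events (AEs) and SAEs from consent to discharge and has the principal investigator judge relationship, severity, expectedness and outcome. Section III.5 lists a telephone call on postoperative day 30 that covers SAEs as well as deaths.

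**The concern.** If the in-hospital objective is to add anything to the 6, 12 and 24-hour objective, it must include units given after 24 hours. The collection plan has no place for those units. Staff who abstract data to the III.5 list would stop at 24 hours, and the analysis would then report a truncated quantity under an in-hospital label.

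This matters for interpretation because the strategy being tested operates mainly during surgery. The whole-stay total is the one listed transfusion objective that could show whether units saved in the operating room stay saved or are given later on the ward or in the ICU. A figure cut off at 24 hours cannot answer that.

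The safety point is separate and smaller. One section closes the SAE window at discharge and another asks about SAEs at day 30, so it is not clear that events first reported at the call are assessed in the same way as in-hospital ones.

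**Working it through.** **Check on the sample size.** The plan's only computed design figure is 110 patients, 55 per group (III.3). Inputs from III.3 are a difference of 3 units, SD 5, alpha 0.025 per outcome and power 80%. The standardized difference is 3/5 = 0.6. A two-sample t-test, two-sided (my assumption, since sidedness is not stated), needs 54.08, rounded up to 55 per group, or 110 in total. Power at 55 per group is 80.7%. The figure reproduces. It uses intraoperative outcomes only and does not depend on anything after 24 hours.

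**Objective against data list.** Split the in-hospital total for one patient into three periods:

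| Period | Part of the in-hospital total? | Units recorded under III.5? |
|---|---|---|
| During surgery (I) | Yes | Yes |
| End of surgery to 24 hours (P) | Yes | Yes |
| 24 hours to discharge (L) | Yes | No |

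The objective needs T = I + P + L. The list supplies R = I + P. For a patient discharged within 24 hours L = 0 and R = T. For every patient who stays longer, R leaves L out.

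Between arms, the mean difference in T equals the mean difference in R plus the mean difference in L. The recorded comparison therefore equals the intended one only if the arms receive the same mean number of late units. If the ROTEM arm receives more late units, R overstates its saving; if it receives fewer, R understates it. The recorded data cannot tell these cases apart.

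**Could another listed item supply L?** Two items in III.5 have no stated window: other hemostatic therapy and the cost assessment. Neither lists transfused units, and the cost objective in II.3 concerns intraoperative transfusion. Length of stay gives the duration of L but not its content. No listed item fills the gap.

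**SAE window.** Section IV runs from consent to discharge. The III.5 call takes place at day 30. For a patient discharged before day 30, the interval from discharge to the call is inside III.5 and outside section IV. An unplanned readmission is an example: the SAE definition includes events that require hospitalization, and a readmission necessarily follows discharge. Planned admissions for an illness that existed before enrolment are not an example, because section IV excludes them from AEs.

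**The case against.** The best defence is that III.5 says what will be recorded, not that nothing else will be. Naming the in-hospital total as an objective signals an intention to obtain it, and later units should be in hospital records. This touches one secondary objective among many. All of that is fair, and it is why the remedy is cheap and the primary result is safe. It does not make the data list complete: a stated collection window still fails to deliver a stated objective.

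A reader might infer four stronger things that the documents do not support.

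- *That half or more of the transfusions are lost.* Objectives refer to day 3, and 24 of 48 hours (50%) or 48 of 72 hours (67%) of postoperative time to that day is uncovered, depending on how day 3 is counted. These are shares of clock time, not of units. They leave out the operation itself, which is fully recorded.
- *That many patients would be wrongly counted as never transfused.* This requires need to mean any transfusion, which is not stated. Eligibility also requires that blood products be anticipated during surgery (III.2), so a first transfusion after 24 hours should be uncommon.
- *That SAEs after discharge go uncollected.* They are a listed item through the day-30 call. The investigator's assessment in section IV is worded for each AE without a time limit of its own, so it can be read to include them. What stands is a mismatch of windows.
- *That the day-3 coagulation objective has the same defect.* Laboratory values are "followed for 24 hours postoperatively", but that objective is conditional: "Compare postoperative coagulation status on days 1 and 3 if available".

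**Conclusion.** The point holds as an inconsistency between II.2 and III.5. Followed as written, the plan cannot produce the in-hospital transfusion total for any patient who stays beyond 24 hours, and it substitutes the intraoperative plus 24-hour total. The conclusion rests on two readings: that the times in III.5 are hours, and that abstraction follows the list as it stands.

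I claim no size in units and no direction of bias, because the documents give no length of stay and no transfusion rate after 24 hours. The two primary outcomes and the sample size are unaffected. The correction should be made because it is cheap and restores an outcome that the trial says it will compare.

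The SAE mismatch between III.5 and IV is a minor consistency point, independent of the transfusion point.

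**What to change.** Extend the transfusion item in III.5 from 24 hours through hospital discharge, taken from existing blood-bank or chart records, and report total in-hospital units by arm. If later units will not be collected, relabel the objective in II.2 as intraoperative plus 24 hours so that the label matches the data.

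Separately, state one SAE window in both III.5 and IV, and say that SAEs first reported at the day-30 call receive the investigator's assessment described in section IV.

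The cost is modest extra chart abstraction and a short amendment. No new visits or samples are needed, since hospital stay is already recorded and the day-30 call is already planned. I assume that transfusion records to discharge are accessible to the study team; the documents do not say.

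### Inclusion criterion 3 admits orthopaedic-only operations, while the objectives and design statement are for spine surgery, so the primary test answers a question the primary objective does not name

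*Combined protocol and SAP*

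**What the plan says.** Criterion 3 in section III.2 admits patients having "elective major spinal, orthopedic, or combined procedures under general anesthesia that are expected to receive intraoperative blood products", provided the operation is expected to last more than two hours. The three procedure types are alternatives. Because combined operations are listed separately, the orthopaedic entry most naturally means an operation with no spinal part. None of the five exclusion criteria concerns procedure type.

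Elsewhere the population is spine only:

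- Primary objective (II.1): intra-operative red cells and plasma "guided with ROTEM versus laboratory coagulation tests in patients undergoing major spinal surgeries".
- Exploratory objective (II.3): "Compare the total costs of intra-operative blood transfusion guided with ROTEM versus laboratory coagulation tests in patients undergoing major spinal surgeries".
- Study design (III.1): a "single center study in patients undergoing elective major spine surgery".
- Figure 1 (VI): the title presents the algorithm as one for spine surgery.

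The sample-size section (III.3) names no procedure. Its calculation is "based on a mean estimated RBC transfusion of 8 units with a conservatively estimated standard deviation of 5", with an expected reduction of 3 units and the same assumptions for plasma. It states "We need 110 patients; 55 patients in each group to achieve 80% power" and "We will test each main outcome between the ROTEM and control groups", at an alpha of 0.025 per outcome. The text available contains no spine-only analysis set.

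**The concern.** Eligibility decides who is randomised, and the objective decides what the result is meant to say. Here the two differ. A screener applying criterion 3 may enrol an orthopaedic-only patient, who then enters a comparison whose stated purpose concerns spine surgery.

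Two things are at stake. First, the primary result would be an average over a mix of procedures that the objective does not mention, and a report that called it a spine-surgery result would misdescribe it. Second, if the investigators wanted a spine-only answer once orthopaedic-only patients had enrolled, that restriction would not be prespecified in the text available, and it would rest on fewer than 110 patients.

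**Working it through.** **1. Reproduce the planned size.** Inputs from III.3: difference d = 3 units, SD s = 5, alpha 0.025 per outcome, n = 55 per arm. The plan does not state sidedness. A two-sided test is assumed because it reproduces the stated number, whereas a one-sided 0.025 test needs only 44 per arm (normal approximation).

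Two-sample t-test: noncentrality = d / (s × √(2/n)), with 2n − 2 degrees of freedom and the critical value at upper tail 0.0125.

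- n = 55: 3 / (5 × √(2/55)) = 3.146; 108 df; critical value 2.273; power 0.8074.
- n = 54: noncentrality 3.118; power 0.7993.

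So 55 per arm is the smallest size that reaches 80%, and 110 is confirmed. There is no arithmetic error.

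**2. Identify whom the stated test covers.** III.3 compares the ROTEM and control groups, needs 55 in each, and restricts by no procedure. The natural reading is everyone randomised, including orthopaedic-only patients admitted by criterion 3. If the effect and SD are the same in those patients, power is 0.8074 whatever their share.

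**3. Identify what that test estimates.** Let q be the orthopaedic-only share and e the mean reduction in those patients. The all-patient difference is (1 − q) × 3 + q × e. It equals the spine difference only if q = 0 or e = 3. The documents give neither q nor e. For example, with q = 0.20 and e = 1.5 (both assumed), it is 0.8 × 3 + 0.2 × 1.5 = 2.70 units. Randomisation keeps this an unbiased estimate for the mix; it is simply not the spine figure.

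**4. Hypothetical: a spine-only comparison within the 110.** The plan does not contain this test. With expected n = 55 × (1 − q) per arm, d = 3, s = 5 and the same formula:

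| Assumed orthopaedic-only share | Expected spine patients per arm | Power |
|---|---|---|
| 0% | 55 | 0.807 |
| 5% | 52.25 | 0.785 |
| 10% | 49.5 | 0.760 |
| 20% | 44 | 0.703 |
| 30% | 38.5 | 0.636 |

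At a 2% share the power is 0.799, so the loss is negligible. Averaging over chance imbalance of spine patients between the arms changes these figures by no more than 0.3 percentage points.

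**The case against.** The strongest reply is that the trial as written loses nothing. The stated test takes all randomised patients, its power is 80.7% under the plan's assumptions, and the lower figures belong to a test the plan does not contain, at shares it does not give. This stands. A reader might infer that the trial is underpowered, or that the plan leaves it undefined which patients the 110 counts. The documents support neither: III.3 most naturally counts and compares everyone randomised.

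A second reply is that the criterion may be loose wording for spine cases, or that orthopaedic-only cases may be rare, since the operation must also be elective, major, longer than two hours and expected to need blood products. This may be so, and it limits the practical consequence. But the criterion is the text that screeners apply, its plain reading admits these patients, and the exclusion left to the investigator's opinion is not a spine-only rule.

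A third reply is that parts of the document are not available: Figure 1 is not shown, and the numbering passes from VI to VIII. Statements that no spine-only analysis is defined are therefore limited to the text available. The conflict between criterion 3 and the objectives is in the current text and does not depend on what is absent.

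Finally, a reader might argue that the two references cited for the sample size, by their titles a cardiac-surgery trial and a trauma study, show that orthopaedic cases invalidate the inputs. They show only that the inputs are not specific to spine surgery.

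**Conclusion.** The inconsistency is real and should be corrected. Criterion 3 admits orthopaedic-only patients; the primary objective, exploratory objective, design statement and algorithm title do not cover them. The consequence lies in the question answered. The all-randomised comparison is unbiased for those enrolled and has about 80.7% power, provided the 3-unit difference and SD of 5 also apply to orthopaedic patients, which the documents do not settle. It should not be read as a finding of bias or of an inadequate sample size.

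The size of the mismatch depends on the orthopaedic-only share, which is unknown and may be small. The spine-only powers in the working are illustrations under assumed shares, not properties of the planned test. Confidence is high in the wording conflict and lower in how much it matters in practice.

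**What to change.** Reconcile the passages in one of two ways:

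1. Limit criterion 3 to major spinal procedures, alone or combined with orthopaedic procedures. The objectives and design statement then stand as they are. The cost is slightly narrower eligibility.
2. Keep criterion 3 and widen the primary objective, exploratory objective and design statement to include orthopaedic surgery. State that the primary comparison covers all randomised patients, and prespecify a secondary spine-only analysis with its lower power at the expected orthopaedic share. The cost is a primary result for a broader population and a less precise answer for spine patients.

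Both are wording changes and leave the 110 unchanged.

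A separate improvement, which does not resolve the conflict, is to prespecify the red cell and plasma comparisons with adjustment for baseline variables already collected under III.5, using robust standard errors. Candidates are procedure type, pre-operative laboratory values and weight. Section III.5 records "Procedure type/reason for surgery, length of surgery" without categories, so the procedure levels must be set in advance. This needs a sentence in the analysis text and a short list of levels. The gain in precision depends on how much variance these variables explain and cannot be quantified from the documents.
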